5.1.5 Planned number of subjects and sites

The planned number of evaluable subjects in the First Period will be a total of 38 subjects for the primary efficacy analysis. Subjects will be enrolled into 4 age groups (1 month to <6 months, 6 months to <1 year, 1 year to <2 years, and 2 years to <4 years), with a minimum of 5 subjects in each age group.

The planned number of monotherapy subjects will be a total of 10 subjects.

It is planned to have those subjects recruited in approximately 20 sites.

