13.8 Planned interim analysis and data monitoring

No interim analyses are planned for this study. For regulatory purposes, a planned data cutoff will be made when the final subject who completes the First Period reaches Visit 13. All the efficacy and safety analysis planned in this protocol will be performed for NDA submission using the interim cutoff data followed by additional cutoff and/or final analysis for long-term follow-up evaluation.

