3.2.2 Schedule of Study Assessments

The study protocol gives the overall study schedule and the permissible intervals for these visits expressed as the number of days relative to Visit 3: Section 5.2 of protocol.

Subjects who were directly enrolled in the Second Period based on the protocol prior to Amendment 3 will also be included in the efficacy and safety analysis with remapping of visit numbers to correspond to the ones for subjects who enrolled in the First Period.

[Table 3–1](#) presents the assessment schedule for subjects:

- who are enrolled prior to Protocol Amendment 3 and are not 48h video-EEG failures; or
- who are enrolled according to Protocol Amendment 3; or
- who are enrolled prior to Protocol Amendment 3 and are 48h video-EEG failures

This document cannot be used to support any marketing application and any extensions or variations thereof.
PUBLIC COPY

Table 3–1: Assessment Schedule

Study Visit	Target day*	Visit Window	Week number
Subjects:			

 • who are enrolled prior to Protocol Amendment 3 and are not 48h video-EEG failures or • who are enrolled according to Protocol Amendment 3 			
Evaluation Period			
Visit 3	Day 1		Week 0
Visit 4	Day 15	Day 11 to Day 19	Week 2
Visit 5	Day 29	Day 25 to Day 33	Week 4
Visit 6	Day 43	Day 39 to Day 47	Week 6
Maintenance Period			
Visit 8	Day 71	Day 64 to Day 78	Week 10
Visit 10	Day 99	Day 92 to Day 106	Week 14
Visit 11	Day 127	Day 120 to Day 134	Week 18
Visit 12	Day 155	Day 148 to Day 162	Week 22
Visit 13	Day 183	Day 176 to Day 190	Week 26
Visit 15	Day 267	Day 260 to Day 274	Week 38
Visit 16	Day 351	Day 337 to Day 365	Week 50
Visit 17	Day 435	Day 421 to Day 449	Week 62
Every 12 weeks			
Subjects:			

 • who are enrolled prior to Protocol Amendment 3 and are 48h video-EEG failures 			
Dose Adjustment Period			
Visit 6	Day 1		Week 0
Visit 7	Day 15	Day 11 to Day 17	Week 2
Visit 8	Day 29	Day 25 to Day 33	Week 4
Visit 9	Day 43	Day 39 to Day 47	Week 6
Maintenance Period			
Visit 10	Day 57	Day 50 to Day 64	Week 8
Visit 11	Day 85	Day 78 to Day 92	Week 12
Visit 12	Day 113	Day 106 to Day 120	Week 16
Visit 13	Day 141	Day 134 to Day 148	Week 20
Visit 14	Day 183	Day 176 to Day 190	Week 26
Visit 15	Day 225	Day 221 to Day 232	Week 32
Visit 16	Day 309	Day 295 to Day 323	Week 44
Visit 17	Day 393	Day 379 to Day 407	Week 56
Every 12 weeks			

Table 3–1: Assessment Schedule

Study Visit	Target day*	Visit Window	Week number

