4.3 Interim Analyses and Data Monitoring

No formal interim analysis is planned for this study. For regulatory purposes, two planned data cut-offs will be made when the final subject who completes the Evaluation Period reaches Visit 13 and Visit 16 in order to obtain 6-month and 12-month exposure data, respectively. All the efficacy and safety analysis planned in the protocol will be performed for NDA submission using the interim cut-off data followed by additional cut-off and/or final analysis for long-term follow-up evaluation.

In addition to above, an interim analysis (IA) was performed for providing PMDA with the latest information to discuss if the study can be discontinued and the application method can be changed to extrapolation strategy based on the results of the IA, which is based on the suggestion at the consultation meeting with PMDA held on [REDACTED] The IA was performed according

to the eCRF snapshot on 04 Jun 2021, in which the data cut-off date was 30 Apr 2021.

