- For each analysis visit, percent reduction in all types of seizure frequency per week from Baseline.

A table Percent Reduction in All Types of Seizure Frequency per Week during Combined First and Second Periods, Adjunctive Therapy Subjects presents summary statistics of subjects on adjunctive therapy, for each analysis visit on the FAS_A.

Note: This is combined over the age categories.

A table Percent Reduction in All Types of Seizure Frequency per Week during Combined First and Second Periods, Monotherapy Subjects presents summary statistics of subjects, on monotherapy, for each analysis visit on the FAS_M.

Note: This is combined over the age categories.

- For each analysis visit, percent reduction in all type of seizure frequency per week from Baseline grouped into 6 categories: <0%, 0% to <25%, 25% to <50%, ≥50%, ≥75%, and 100%.

A table Percent Reduction in All Types of Seizure Frequency per Week Grouped into 6 Categories During Combined First and Second Periods, Adjunctive Therapy Subjects, presents the number and percentage of subjects on adjunctive therapy within each of the above defined six categories for all analysis visits on the FAS_A.

Note: This is combined over the age categories.

A table Percent Reduction in All Types of Seizure Frequency per Week Grouped into 6 Categories During Combined First and Second Periods, Monotherapy Subjects, presents the number and percentage of subjects on monotherapy within each of the above defined six categories for all analysis visits on the FAS_M.

Note: This is combined over the age categories.

The following other efficacy variable is only applicable to Monotherapy:

- Percent of subjects who are continuously 6-months seizure-free monitored by the patient diary.

A subject is considered 6-months seizure free if they are seizure free for at least $26 \times 7 = 182$ consecutive days during the combined period of Evaluation Period + Dose adjustment Period + Maintenance Period, otherwise they are not considered seizure free.

The seizure free time interval must not contain days for which seizure data are missing, ie, “Not done” was checked on the Seizure Count CRF or seizure information is missing otherwise, eg because the complete and required CRF module was not filled out for a certain visit.

Subjects who received less than 182 days study medication are counted as not having achieved 6-months seizure freedom.

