Missing seizure dates and dates for “not done” rows (in the following both are called “row”) are handled as follows:

- If the row date is missing completely (no entry), two cases can occur

1. The missing row date is in the first row of the CRF.
In this case, the visit date of the visit before the documentation visit is imputed.
2. The missing row date is not the first row of the CRF.
In this case, the date of the day after the last entry in the rows before the row with the missing date is imputed.

- If the row date is missing completely (“UNK”, ie, unknown), then the date of the visit before the documentation visit is imputed, independent of the row being the first row or a later one.
- If the year and month of a row date is present but the day is missing, then the same imputation as for a completely missing row date is performed first. If the imputed date is before the first of the month that is documented, then the first day of the month is used.
- If the year of a row date is present but the month is missing, then the same imputation as for a completely missing date is performed first. If the imputed date is before the first of the year that is documented, then the first day of the year is used.

A table Percent and Number of Subjects Who are continuously 6-Months Seizure-Free Monitored by Patient Diary During the Evaluation, Dose-adjustment and Maintenance Period presents the number and percentage of subject on monotherapy who are continuously 6-months seizure-free on the FAS_M.

Note: This is combined over the age categories.

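### At the Visit 13 cut-off, monotherapy children still on treatment but with too little calendar time for a 182-day run count as not seizure-free, so the 6-month percentage can only be biased downward

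*SAP*

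**What the plan says.** **The variable.** SAP 8.3.2 defines 6-month seizure freedom for monotherapy children only. It requires at least 26 × 7 = 182 "consecutive days during the combined period of Evaluation Period + Dose adjustment Period + Maintenance Period". On the diary it says: "The seizure free time interval must not contain days for which seizure data are missing". A seizure page not completed for a visit counts as missing. It then adds: "Subjects who received less than 182 days study medication are counted as not having achieved 6-months seizure freedom". The table gives the number and percentage of children "who are continuously 6-months seizure-free on the FAS_M". Nothing separates a child who stopped or had seizures from one still on treatment when the data are cut.

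**The timing.** Under Protocol 13.8, "a planned data cutoff will be made when the final subject who completes the First Period reaches Visit 13". SAP 1 and 4.3 plan two cut-offs, at Visit 13 and at Visit 16. SAP Table 3-1 (section 3.2.2) permits Visit 13 on "Day 176 to Day 190", Visit 15 on Day 260 to 274 and Visit 16 on Day 337 to 365. SAP 4.3 states: "All the efficacy and safety analysis planned in the protocol will be performed for NDA submission using the interim cut-off data". A further cut-off or a final analysis is to follow.

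**The group.** Protocol 5.1.5: "The planned number of monotherapy subjects will be a total of 10 subjects". Both documents class the percentage among the other efficacy variables. It is descriptive, with no test and no threshold.

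**The concern.** The run that defines success is almost exactly as long as the follow-up guaranteed at the first cut-off. A child at Visit 13 can succeed only by being seizure-free from about the first dose. Inclusion criterion 7a requires at least two partial seizures in each of the two baseline weeks, and Protocol 5.1.2 raises the dose at 2-week intervals while seizure freedom has not been reached. Response after a dose step is therefore an expected pattern, and a late-enrolled child who responds that way cannot yet be counted.

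The monotherapy group has no primary variable and no First Period secondary variable (Protocol 4.1.2), and this percentage is its measure of sustained response. In about 10 children, a single child misclassified by the calendar visibly moves it.

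**Working it through.** **1. The plan's own days.** Target day = 7 × week + 1. Visit 13 (Week 26): 183, ± 7 gives 176 to 190. Visit 15 (Week 38): 267, ± 7 gives 260 to 274. Visit 16 (Week 50): 351, ± 14 gives 337 to 365. All agree with SAP Table 3-1.

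**2. Latest day on which a countable run can start** = last diary day − 182 + 1.

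| Last diary day | Latest start |
|---|---|
| 176 (Visit 13, earliest) | −5, impossible |
| 182 | Day 1 |
| 183 (Visit 13, target) | Day 2 |
| 190 (Visit 13, latest) | Day 9 |
| 260 (Visit 15, earliest) | Day 79 |
| 337 (Visit 16, earliest) | Day 156 |
| 351 (Visit 16, target) | Day 170 |

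Days 176 to 181, 6 of the 15 permitted Visit 13 days, leave no possible success.

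**3. Day on which a run is complete** = start + 181. A start on Day 15 gives Day 196, Day 29 gives Day 210, and Day 43 gives Day 224. All fall after the Visit 13 window.

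**4. Who is exposed.** Let the last child's Visit 13 fall on Day D. A child first dosed k days earlier is then at Day D + k.

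- Fewer than 182 days: k ≤ 181 − D. At D = 176 this is k ≤ 5; from D = 182 on, nobody.
- Fewer than 224 days (room for a run starting by Day 43): k ≤ 223 − D. At D = 183 this is k ≤ 40, about 6 weeks.
- Diaries are collected at visits, and Visit 15 comes 267 − 183 = 84 days after Visit 13. If later diary pages are not in the data at cut-off, the countable diary ends at Visit 13 and the entry window widens to about 12 weeks. The documents do not say whether those pages would be in.

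**5. Size.** One eventual success missed in 10 children is 1/10 = 10 points. The number of late entrants is not given. For scale only, assume 38 + 10 = 48 children, the last one plus 47 spread evenly over T days, with monotherapy children mixed in proportion. The expected number of monotherapy children in the last w days is (1 + 47w/T) × 10/48.

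| Entry window w | T = 730 days | T = 1460 days |
|---|---|---|
| 42 days | 0.77 | 0.49 |
| 84 days | 1.3 | 0.77 |

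These are children at risk, not false failures. If half of them would eventually succeed (assumption) and none could yet be counted, the 42-day row gives 0.49 × 0.5 × 10 = 2.5 to 0.77 × 0.5 × 10 = 3.9 points. The 84-day row gives 3.9 to about 6.7 points. If no monotherapy child enrols late, the effect is 0.

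**The case against.** - **The sentence on fewer than 182 days of medication adds little.** A child with less than 182 days fails the run-length requirement anyway. On its own the sentence reaches only children dosed at most 5 days before a last child seen on Day 176. This stands. The cause is short follow-up set against a run that may start late, with every FAS_M child in the denominator.
- **Visit 16 repairs it.** This largely stands: with diary to Day 337, a run starting as late as Day 156 counts. But Protocol 13.8 names only Visit 13, and the SAP does not say which cut-off carries this variable.
- **Counting non-completers as failures is an ordinary conservative convention.** This stands for children who stopped, and the proposal keeps it for them. It is a weaker argument for a child still on treatment.
- **The stakes are low.** This stands. The variable is descriptive and the rule can only understate efficacy. The dated seizure listing (SAP 8.4) and the exposure listing (SAP 10.1.3) would let a careful reader spot a truncated child among about 10.
- **Even accrual over 2 to 4 years is guesswork.** This stands. Protocol 2 describes great difficulty in recruiting. The protocol dates from February 2017, and at the data cut of 30 Apr 2021 stopping the study was still under discussion (SAP 2 and 4.3). Slower accrual makes the figures smaller, while the diary gap after Visit 13 makes them larger.

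**Conclusion.** The point holds in a limited form. At the Visit 13 cut-off, continuing monotherapy children with too little calendar time are scored as not seizure-free, and this can only lower the percentage. The direction follows from the definition. The size does not: it may be zero, and it is 10 points for each eventual success missed if FAS_M is 10. The bias largely disappears at Visit 16. It is a minor point of reporting.

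A reader might infer that the submission figure is too low by design, or that the 0.5 to 0.8 exposed children in the 42-day row mean an understatement of 5 to 8 points. The documents support neither. A child seizure-free from Day 1 or 2 passes at the target Day 183, earlier entrants have longer follow-up, and the last completer may be an adjunctive child. Turning exposed children into points assumes that all of them would later succeed and that none can yet be counted.

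**What to change.** In SAP 8.3.2, keep the percentage as written and add one row at each cut-off with:

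- (a) the number of children still on treatment whose time from first dose to cut-off is too short;
- (b) the percentage among all children with enough potential follow-up.

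Define potential follow-up only by the dates of first dose and cut-off: at least 182 days and, as a second threshold, at least 224 days (room for a run starting by Day 43). Within that denominator, children who stopped early remain failures. State that the Visit 16 cut-off gives the main estimate of this variable.

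The date-only definition matters. If a child were set aside because the current run began too late, evaluability would depend on when seizures occurred. At Day 183 a child seizure-free from Day 1 would enter as a success, while a continuing child with a seizure on Day 10 would drop out of the denominator, which biases the percentage upward.

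The cost is a few sentences and one table row. The denominator of the added percentage is slightly smaller at the first cut-off. The date thresholds do not correct for diary pages not yet collected after Visit 13, which is a further reason to rest the main estimate on Visit 16.

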4.2.1 General Imputation Rule for Incomplete Dates

Where necessary for the calculation of derived variables, partial dates will be completed using the earliest calendar date based on the partial date provided. This rule is valid for all partial dates with the exception of the following:

- Start and stop dates of concomitant medication, [Section 4.2.2](#)
- Start and stop dates of Adverse Events, [Section 4.2.3](#)

Completely missing dates will not be replaced and the corresponding derived variables will be set to missing.

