8.1 Statistical Analysis of the Primary Efficacy Variable

8.1.1 Primary Efficacy Variable for Adjunctive Therapy

First Period

The primary efficacy variable for subjects on adjunctive therapy for the First Period is the percent reduction in partial seizure frequency per week from Baseline to Study Visit 6. In order to include the EEG failures subjects who were enrolled prior to Protocol Amendment 3, analysis visit will be used therefore the primary efficacy variable is presented as the percent reduction in partial seizure frequency per week from Baseline to Analysis Visit 3.

The percent reduction in partial seizures per week from Baseline to Study Visit 6 (Analysis Visit 3) will be calculated as:

$$\frac{\text{Number of partial seizures per week at Baseline} - \text{Number of seizures per week at Analysis Visit 3}}{\text{Number of partial seizures per week at Baseline}} \times 100$$

The number of partial seizures per week at Baseline will be based on the Retrospective Baseline seizure counts (during the 2 weeks prior to Study Visit 1) + Selection Period (Study Visit 1 and Study Visit 2*), see Section 3.3, and will be calculated as:

[total number of partial seizures entered on the DRC starting at the 2 weeks prior to Study Visit 1 until Study Visit 3 divided by the number of days on which data was entered on the DRC] $\times 7$.

*Study Visit 2 is only applicable for those subjects enrolled prior to Protocol Amendment 3.

The number of seizures per week at Study Visit 6 (Analysis Visit 3) will be based on the seizure count from Analysis Visit 2 to Analysis Visit 3 and will be calculated as:

[total number of partial seizures entered on the DRC during the period starting 1 day after Study Visit 5 (Analysis Visit 2) through Study Visit 6 (Analysis Visit 3) divided by the number of days, within this period, on which data was entered on the DRC] $\times 7$

Those seizure free days (ie, seizure count is 0 and there is no entry of DRC data) will be included into denominator. Data was NOT entered on DRC only refer to the situation that “Not Done” was ticked on CRF “Seizure Count” page

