Number of partial seizure frequency per week, as collected on the DRC, is calculated at Analysis Visit x, x=1, 2, 3, 4, ..., as:

Number of partial seizures per week at Analysis Visit x = [total number of partial seizures entered on the DRC during the period starting 1 day after Analysis Visit x-1 through Study Day of Analysis Visit x divided by the number of days, within this period, on which data was entered on the DRC] x 7. Those seizure free days (i.e. seizure count is 0 and there is no entry of DRC data) will be included into denominator. Data was NOT entered on DRC only refer to the situation that “Not Done” was ticked on CRF “Seizure Count” page.

The following summary tables based on the FAS_A will be presented:

- Percent Reduction in Seizure Frequency per Week, by Analysis Visit, Adjunctive Therapy Subjects
- Percent Reduction in Seizure Frequency per Week Grouped into 6 Categories by Analysis Visit, Adjunctive Therapy Subjects

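### Seizure rows of unknown date are dated to the visit before the interval they were documented for, so a counted 6-month seizure-free run can contain the seizure

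*SAP*

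**What the plan says.** SAP 8.3.2 gives date rules for seizure rows and Not Done rows under the monotherapy 6-month seizure-freedom variable.

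- Row marked UNK: "then the date of the visit before the documentation visit is imputed, independent of the row being the first row or a later one".
- Row with no date entry, first on the form: "In this case, the visit date of the visit before the documentation visit is imputed".
- Row with no date entry, later on the form: "the date of the day after the last entry in the rows before the row with the missing date is imputed".
- Row with a known year, or year and month: the same imputation is made, then moved forward to the first of that year or month if it fell earlier.

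The same section requires at least 182 consecutive seizure-free days within the combined Evaluation, Dose Adjustment and Maintenance Periods. It bars from the run any day with missing seizure data. It says nothing about an interval known to hold a seizure of unknown date.

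For weekly frequencies, SAP 8.2.1 counts seizures "during the period starting 1 day after Analysis Visit x-1 through Study Day of Analysis Visit x", and SAP 8.1.1 starts the Visit 6 period in the same way, one day after Visit 5. Neither section has its own rule for undated seizures. The general rule in SAP 4.2.1 is that "partial dates will be completed using the earliest calendar date based on the partial date provided". Under that rule completely missing dates are not replaced and the derived variables are set to missing. Its listed exceptions cover concomitant medications and adverse events, not seizure rows.

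**The concern.** The documentation visit is known, so the interval in which the seizure occurred is known too. The UNK and blank-first-row rules discard that information and place the event on the one day just before the interval. A single imputed date cannot be cautious for both the run before it and the run after it: the earliest date shortens the earlier run and lengthens the later one. A monotherapy child can therefore be reported as 6-month seizure-free over days in which the CRF records a seizure.

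The same applies to an undated Not Done row. It is also moved out of its interval, so days that may be missing are treated as observed, which weakens the section's own bar on missing days.

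The rule opens in general terms but sits under a monotherapy-only variable. It is therefore also unclear which rule dates an undated seizure for the adjunctive weekly counts, including the primary one.

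**Working it through.** **Inputs.** Visit target days from SAP Table 3-1: Visit 3 = Day 1, Visit 4 = 15, Visit 5 = 29, Visit 6 = 43, Visit 8 = 71, Visit 12 = 155, Visit 13 = 183, Visit 16 = 351. Run length from SAP 8.3.2. Ten planned monotherapy subjects from protocol 5.1.5. Entry minimum of 2 partial seizures in each 7-day period from protocol 6.1, criterion 7a.

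**The plan's own figure.** 26 × 7 = 182 days, as stated.

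**Seizure freedom, UNK row documented at Visit 13.** Assume an earlier dated on-treatment seizure, so that no earlier run qualifies.

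- Possible true days: 156 to 183, that is 28 days.
- Imputed day: 155. Counted run: Days 156-337 = 337 − 156 + 1 = 182 days, so the child qualifies before Visit 16 (Day 351).
- With the true seizure on Day d, the run to Day 351 is 351 − d days. This is at least 182 only if d ≤ 169.
- Days 156-169 (14 days): status at Day 351 is correct. Days 170-183 (14 days): status is false.
- Run guaranteed by the records: Days 184-351 = 168 days.

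**Seizure freedom, UNK row documented at Visit 4.** Imputed to Day 1. Days 2-183 = 182 days, so the child qualifies at Visit 13. The true run to Day 183 is 181 days if the seizure fell on Day 2 and 168 days if it fell on Day 15. Data ending at Day 183 would give a false status for every possible true day in that interval.

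**Opposite direction.** A child otherwise seizure-free from Day 1, with a true seizure on Day 183 documented as UNK at Visit 13, has a true run of Days 1-182 = 182 days. Dated to Day 155, the run is Days 1-154 = 154 days.

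**Size for this variable.** 1/10 = 10 percentage points per child.

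**Weekly counts, only if the same imputed dates are used.**

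- Visit 6 window: Days 30-43, 14 days. A UNK seizure documented at Visit 6 is dated Day 29 and leaves the window.
- A UNK seizure documented at Visit 8 is dated Day 43 and enters the window. Its source interval is 71 − 43 = 28 days, against 43 − 29 = 14 days for the outflow.
- The denominator does not change, because "Those seizure free days (ie, seizure count is 0 and there is no entry of DRC data) will be included into denominator".
- One seizure in 14 days is 0.5 per week. The shift in that child's percent reduction is 0.5/b × 100 = 50/b points, with b the baseline rate per week:

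| b per week | shift, points |
|---|---|
| 2 (entry minimum) | 25.0 |
| 4 | 12.5 |
| 7 | 7.1 |
| 14 | 3.6 |

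The shift is upward for a seizure lost from Visit 6 and downward for one gained.

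**The case against.** The strongest reply is that the certain effect is confined to an untested other efficacy variable in about ten planned children, and that the rule is often right there: in the Visit 13 example, half of the possible true days give the correct status at Day 351. Even a Day 183 seizure is followed by 182 free days by Day 365, the last day of the Visit 16 window. Blank later rows usually stay inside their interval, partial dates are floored to the documented month or year, and SAP 3.4 provides for queries and agreement on data handling before lock. All of this stands. It limits the size but does not make the rule correct.

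A reader might go further and infer that the primary Visit 6 result is biased in favour of levetiracetam. The documents do not support that, for four reasons.

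- The SAP does not say that these imputed dates feed the adjunctive weekly counts.
- If they do, Visit 6 also gains seizures documented at Visit 8. At a constant rate of undated rows, a 28-day inflow against a 14-day outflow would work against levetiracetam in children who continue.
- If SAP 4.2.1 governs instead, a fully missing date may set the derived value to missing, which is not the same as a lower count.
- Inflation of baseline by seizures dated to Visit 3 is not established. SAP 8.1.1 counts until Visit 3, but SAP 3.2.1.2 ends the Selection Period one day before it.

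Nor should a 25-point shift in one child be set beside the 15% threshold. The threshold applies to the lower confidence limit of the overall median, based on order statistics, with 38 subjects planned.

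**Conclusion.** The point holds for 6-month seizure freedom. The stated rule can place a recorded seizure inside a run that is counted as seizure-free, and it can also shorten a true run. In the Visit 13 example the counted run is 182 days where the records guarantee 168. This assumes visits on target days, no earlier qualifying run and follow-up to Day 351. Each affected child is worth 10 percentage points if ten monotherapy subjects are enrolled.

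For the weekly frequencies, including the primary variable, the finding is an unresolved ambiguity: the SAP does not state which rule dates an undated seizure, and neither candidate rule reliably keeps it in its documentation interval. Direction and size cannot be derived, because the documents do not give the rate of undated rows.

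**What to change.** Amend SAP 8.1.1, 8.2.1 and 8.3.2 as follows.

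1. Weekly frequencies: count an undated or partly dated seizure in the interval of the visit at which it was documented, from the day after the previous visit through the documentation visit.
2. Seizure freedom: treat every day of that interval not excluded by the partial date as not seizure-free. For a fully undated row, a new run can then start only on the day after the documentation visit.
3. Undated Not Done rows: handle them in the same way, with the possible days of the interval treated as missing.
4. State that this overrides SAP 4.2.1 for seizure rows.

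The cost is a few lines of wording and programming, with no new data. The downside is that item 2 is a conservative convention. In the Visit 13 example a new run would start on Day 184 and reach 182 days only on Day 365. A child whose seizure fell on Days 156-169 would then be counted as seizure-free later than is true, or not at all by a given cut-off. The seizure-freedom percentage may fall slightly.
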